#### 3.2. All Screened Set

The All Screened Set will include every patient who has signed the informed consent form.

The All Screened Set will be used for summaries of disposition and the associated listings.

#### 3.3. On-Treatment Analysis Set

On-Treatment analysis set will consist of all randomized patients who received at least one dose of study drug. Patients will be considered to be on-treatment through the EoT date as outlined in Section 3.1. On-Treatment Analysis Set patients are analyzed according to the actual treatment they received. The On-Treatment Analysis Set will be used for summaries and analysis of demographics and baseline characteristics, treatments and medications, safety endpoints, secondary endpoints, exploratory endpoints and will be the primary analysis set for the analysis of the primary endpoint.

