## 6.2 Treatment assignment and randomization

Patients will be randomized on Day 1 to one of the following treatment arms in a 1:1:1 ratio:

- Abelacimab (MAA868) 90 mg s.c. monthly
- Abelacimab (MAA868) 150 mg s.c. monthly
- Rivaroxaban 20 mg p.o. once per day with evening meal

[Note: Patients with a CrCl  $\leq$  50 ml/min by the Cockcroft-Gault equation will have a dose adaptation to rivaroxaban 15 mg p.o. daily.]

Randomization into treatment groups will be stratified by the use of concomitant antiplatelet use at baseline (yes/no) and renal function (CrCl  $\leq$  50 ml/min or CrCl  $>$  50 ml/min). Patients randomized to the rivaroxaban arm may be dose adjusted between the 15 mg dose and 20 mg doses depending on CrCl values.

Once a subject is stratified and randomized, the subject will stay in that starting stratum, randomized treatment group, and treatment regimen for analyses purposes even if their dose is subsequently adjusted.

Once Investigators have ascertained that the patient is eligible for the study, they will contact the Interactive Web or Voice Response System (IxRS) before the first administration of study drug. The IxRS will require the following information in order to randomize a patient to the correct stratification: year of birth, CrCl (Cockcroft-Gault) and whether the patient takes antiplatelet medications (i.e., aspirin and/or a P2Y12 inhibitor) as a concomitant medication. The IxRS will allocate the treatment group assignment for the patient.

Emergency unblinding will be done through the IxRS system. The treatment code should not be broken except in medical emergencies when the appropriate management of the patient requires knowledge of the treatment assignment. The decision of whether or not to unblind lies with the investigator and it is the sole responsibility of the investigator to determine the need for immediate unblinding. However, if time and circumstances permit, the Investigator is encouraged to contact the [REDACTED]  
[REDACTED]  
[REDACTED]

The specifications for generation of the randomization schedule will be prepared by the study biostatistician and the contract research organization (CRO) in charge of the IxRS. An independent biostatistician, not otherwise part of the clinical study execution team, will generate the randomization schedule. The randomization numbers will be generated to ensure that treatment assignment is unbiased.

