### **10.1 Analysis sets**

- On-Treatment: will consist of all randomized patients who received at least one dose of study drug. Patients will be considered to be on-treatment if within 60 days of their last dose of study drug up to the EoT visit of the randomized treatment period.
- Intent-to-Treat (ITT): all patients randomized and dosed to be analyzed according to randomized treatment assignment. Events occurring from randomization through EoS of the randomized treatment period will be included in the analysis.
- Per Protocol: All randomized patients with a treatment compliance rate of at least 80% and do not have any major protocol violations as defined in the final SAP.
- On-Treatment Extension: will consist of all patients who received at least one dose of abelacimab in the extension period. Patients will be considered to be on-treatment if within 60 days of their last dose of study drug to the EoE visit of the extension period.

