### **10.4 Analysis of the primary variable(s)**

The primary analysis will compare each abelacimab regimen with rivaroxaban for the time to first occurrence of major or CRNM bleeding in the On-Treatment Analysis Set. For each treatment regimen, the event rate will be estimated with 95% confidence intervals (CIs). The time to first event will be analyzed using the Cox proportional hazards model including treatment and the following two stratification factors as covariates:

- Planned use of concomitant antiplatelet medication use (e.g., aspirin and/or P2Y12 inhibitor) for the duration of the trial
- CrCl (Cockcroft-Gault)  $\leq 50$  ml/min

The hazard ratios (HR) with 95% CIs will be reported for both doses of abelacimab vs. rivaroxaban. A significance level of  $\alpha=0.05$ , without adjustment for multiplicative testing, will be used. A sensitivity analysis will be performed in the ITT population.

The proportional hazards assumption in the Cox model will be assessed. A piecewise Cox model will be considered given evidence of non-proportional hazards.

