#### 3.4. Intent-to-Treat (ITT)

The ITT will consist of all patients randomized and dosed to be analyzed according to randomized treatment assignment. Events occurring from randomization through EoS will be included in the

analysis. The ITT analysis set will be used to perform a sensitivity analysis of the primary, secondary, and exploratory endpoints.

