### **6.10. Exploratory Biomarkers**

## **7. Changes in the Conduct of the Study or Planned Analysis**

There were no changes in the conduct of the study at the time of preparing this SAP.

There were no changes in the analysis planned in the protocol of the study at the time of preparing this SAP.

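### SAP 3.3 groups the primary bleeding analysis by treatment actually received; if any patient received something other than the assigned treatment, the primary test would not compare the arms as randomized

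*SAP*

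**What the plan says.** - **SAP 3.3** says "On-Treatment Analysis Set patients are analyzed according to the actual treatment they received". The same section says the set "will be the primary analysis set for the analysis of the primary endpoint", and uses it for secondary and exploratory endpoints and for the safety summaries.
- **Protocol 6.2** first allows rivaroxaban patients to move between 15 mg and 20 mg with creatinine clearance. It then says that once randomized "the subject will stay in that starting stratum, randomized treatment group, and treatment regimen for analyses purposes even if their dose is subsequently adjusted".
- **Protocol 10.1** defines the set by dosing, "On-Treatment: will consist of all randomized patients who received at least one dose of study drug", and adds a 60-day window after the last dose. It does not say by which arm these patients are analysed; randomized assignment is mentioned only for ITT. Protocol 10.4 places the primary comparison in the On-Treatment set and adds no grouping rule.
- **SAP 3.4 and 3.5** group the other two sets as randomized. For ITT, "The ITT will consist of all patients randomized and dosed to be analyzed according to randomized treatment assignment", with events counted through EoS. The Per Protocol Set is also analysed by randomized treatment.
- **SAP 7** states "There were no changes in the analysis planned in the protocol of the study at the time of preparing this SAP".
- **The SAP addendum**, written after database lock, revises the ITT definition (2.4) and notes that this departs from Protocol 10.1. It does not touch the grouping rule in SAP 3.3.

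**The concern.** As-treated grouping is ordinary for adverse-event tables. Here the same rule also governs a superiority test and the hazard ratios reported for each dose. A p-value from a randomized trial rests on arms formed by randomization. Moving patients according to what they later received can make the arms differ in underlying bleeding risk.

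The rule is also incomplete. Abelacimab is given monthly from kits assigned by IxRS, and the dose is blinded (Protocol 6.3 and 6.4.1). Protocol 8.5 provides for recording treatment errors. The SAP does not say how to classify a patient who received one wrong-dose kit among many injections: by first dose, by most doses, or by any dose. That leaves a choice open inside the primary analysis.

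**Working it through.** **1. Reproduce the plan's own figure.** Inputs from SAP 2.3 and Protocol 6.2: hazard ratio (HR) 0.60, two-sided alpha 0.05, power 80%, allocation 1:1:1, 166 events in total.
- Schoenfeld, per pair: 4 × (1.96 + 0.8416)² / (ln 0.60)² = 120.3, rounded up to 121.
- Share of all events falling in one abelacimab–rivaroxaban pair: (1 + 0.60)/(1 + 2 × 0.60) = 1.6/2.2 = 72.7%.
- Total: 121/0.727 = 166.4, against 166 stated. Power at 166 × 0.727 = 120.7 events is 80.1%.

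The planned size reproduces and does not depend on the grouping rule.

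**2. Expected events per arm.** Rivaroxaban 166/2.2 = 75.5; each abelacimab arm 0.60 × 75.5 = 45.3.

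**3. Effect of one reassigned event, person-time held fixed.**
- From rivaroxaban to an abelacimab arm: (46.3/45.3) × (75.5/74.5) = 1.036, so 0.60 becomes about 0.62.
- Between the two doses: 1/45.3 = 2.2%, raising one dose's HR and lowering the other's.

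**4. Scale.** SE(log HR) = √(1/45.3 + 1/75.5) = 0.188, so the 95% CI around 0.60 is about 0.42 to 0.87. One event moved to or from rivaroxaban is ln(1.036)/0.188 = 0.19 SE; one moved between doses is ln(1.022)/0.188 = 0.12 SE. These are per event, not per patient: about 45/400 = 11% of abelacimab patients would have an event.

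**5. Illustration of bias.** Assumptions, not trial data: 400 per arm (1,200/3), true HR 0.60, equal person-time, and m patients randomized to one abelacimab arm who actually received rivaroxaban. Their underlying bleeding risk is k times average, and the arm as randomized has average risk 1.
- As randomized: HR = 0.60 + 0.40 × mk/400.
- As treated: HR = 0.60 × [(400 − mk)/(400 − m)] / [(400 + mk)/(400 + m)].

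| m | k | As randomized | As treated |
|---|---|---|---|
| 0 | any | 0.600 | 0.600 |
| 4 (1%) | 1 | 0.604 | 0.600 |
| 4 (1%) | 3 | 0.612 | 0.576 |
| 20 (5%) | 0.5 | 0.610 | 0.631 |
| 20 (5%) | 1 | 0.620 | 0.600 |
| 20 (5%) | 3 | 0.660 | 0.490 |

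In this model the as-treated HR stays at 0.60 when mis-treatment is absent or unrelated to risk. It moves below 0.60, in abelacimab's favour, when higher-risk patients are mis-treated, and above it when lower-risk patients are. The as-randomized HR moves only towards 1.

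**6. Does a planned analysis isolate the grouping?** SAP 6.6.2 lists four.
- ITT changes the grouping and also moves censoring from EoT to EoS. Addendum 2.4 appears to drop the dosing requirement as well, though the extracted text there is damaged.
- The Per Protocol analysis uses randomized treatment but adds a compliance threshold and deviation exclusions.
- The other two, censoring at other anticoagulation and pooling the doses, stay in the as-treated set.

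None changes the grouping alone.

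**The case against.** **Protocol 6.2 may be narrower than it looks.** Its sentence follows the 15/20 mg text and ends by referring to dose adjustment. Read that way, it only stops a change in renal function or tablet strength from moving a patient, and SAP 3.3 does not contradict it: a patient switched to 15 mg still received rivaroxaban. This stands as a possible reading. The sentence nevertheless names the randomized treatment group and analysis without restriction, so the two texts need reconciling.

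**The protocol is silent and defers to the SAP.** Protocol 10.1 sets no grouping for the On-Treatment set, and Protocol 10 leaves further detail to the SAP. A reader might infer that the SAP 7 statement is false. The documents do not establish that, because filling a gap is not plainly a change. They do show a rule for the primary test that the protocol does not contain.

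**The primary endpoint is a safety endpoint.** Protocol 1.2.2 describes it so, and as-treated grouping is a recognised choice for on-treatment safety. That is fair for description; it is weaker support for a hypothesis test.

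**A randomized-arm analysis exists.** ITT covers the primary, secondary and exploratory endpoints. For patients entering the extension, addendum 2.1 sets EoS to the day before the EoT visit, so the two windows nearly coincide for them. They still differ for others, including patients who stopped early, so a gap between the two results could not be attributed to grouping.

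**Misallocation may be rare or nil.** Kits come through IxRS, and a monthly injection is hard to confuse with a daily tablet. This stands, and it limits the likely size.

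**Conclusion.** The point holds conditionally. SAP 3.3 permits a primary comparison that departs from the randomized arms, under a rule absent from Protocol 10.1, in tension with Protocol 6.2, and undefined for mixed dosing.

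A reader might go further and infer that the primary test is not a comparison of randomized groups. The documents do not support that. The two rules differ only for patients whose actual and assigned treatments differ, and no such patient is reported. With none, the result is identical.

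The size is therefore unknown. Per reassigned event it is about 3.6% of the HR against rivaroxaban, or about 2.2% on each dose's HR for a swap between doses, both small beside a standard error of 0.188. The larger shifts in the illustration need both an assumed 5% misallocation and a strong link to bleeding risk.

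The case for changing the rule rests on its low cost and on removing an avoidable source of bias, not on a demonstrated effect. Regrouping would not make this a full ITT analysis: the set still requires a dose and censors at the EoT date.

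**What to change.** In SAP 3.3 or an addendum:
1. State that the primary, secondary and exploratory bleeding time-to-event analyses in the On-Treatment set use the randomized group, with censoring at the EoT date.
2. Keep actual treatment for adverse-event, laboratory and exposure tables, and define it for patients who received more than one abelacimab dose level or an isolated wrong kit.
3. Report by arm how many patients' actual and randomized treatments differ. If there are none, one line closes the matter.

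The cost is a few sentences, one grouping variable in the programs and a rerun, with no new data. The SAP was final on 24Jul2023 and the database was locked on 08Mar2024, so a change made now is a post-lock change to the primary analysis. It should be declared as such, with the as-treated result specified in SAP 3.3 reported alongside. If the sponsor prefers to keep the as-treated rule, it should be reconciled with Protocol 6.2 and declared, and the On-Treatment analysis by randomized arm added as a sensitivity analysis.

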#### 3.4. Intent-to-Treat (ITT)

The ITT will consist of all patients randomized and dosed to be analyzed according to randomized treatment assignment. Events occurring from randomization through EoS will be included in the

analysis. The ITT analysis set will be used to perform a sensitivity analysis of the primary, secondary, and exploratory endpoints.

### **3.5. Per Protocol Set**

The Per Protocol Set (PPS) will consist of all randomized patients with a treatment compliance rate of at least 80% and do not have any important protocol violations. The important protocol violations will be identified, documented, and finalized by the clinical study team prior to the final analysis. PPS patients are analyzed according to their randomized treatment.

Protocol deviations are defined as any change, divergence, or departure from the study design or procedures defined in the study protocol. Important protocol deviations are a subset of protocol deviations which may significantly impact the correctness, accuracy, and / or reliability of the study data or that may significantly affect a subject's rights, safety, or well-being and are outlined in Section [3.5.1](#).

#### **3.5.1. Important Protocol Deviations Leading to Exclusion from the PPS**

Deviations from the protocol, as defined in the protocol deviation plan, will be documented by the study monitors and project management throughout the study period.

Only those important protocol deviations considered to have a major effect on the primary endpoint will lead to complete exclusion of the patient from the PPS. For the purposes of this study, the criteria specified in a separate document have been identified as important protocol deviations leading to exclusion from the PPS. It is considered that the occurrences of any of these criteria might have an important influence on the primary endpoint.

Criteria which require clinical or medical monitoring interpretation will be reviewed prior to database lock. All important protocol deviations leading to exclusion from the PPS occurring during the study will be reviewed and approved by Anthos prior to database lock and identified before data are unblinded.

### **3.6. On-Treatment Extension**

The On-Treatment Extension (OTE) analysis set will consist of all patients who received at least one dose of study drug during the extension period.

### **3.7. Pharmacokinetics Analysis Set**

The Pharmacokinetic (PK) Analysis Set will include all patients who received at least 1 dose of abelacimab and have at least 1 quantifiable PK concentration. PK Analysis Set patients are analyzed according to their actual treatment received.

### **3.8. Pharmacodynamics Analysis Set**

The Pharmacodynamics (PD) Analysis Set will include all patients who received at least 1 dose of abelacimab and have at least 1 quantifiable PD data. PD Analysis Set patients are analyzed according to their actual treatment received.

## 4. Estimands

The ICH E9 (R1) addendum on estimands and sensitivity analysis in clinical trials to the guideline on statistical principles for clinical trials came into effect on 30 July 2020. This section addresses the construction of estimands for the primary and secondary objectives.

### 4.1. Estimands for the primary objective

Each estimand is defined according to the following five attributes:

- 1) The **treatment** condition of interest, and as appropriate, the alternative condition to which comparison will be made.
- 2) The **population** of patients targeted by the clinical question.
- 3) The **variable** (or endpoint) to be obtained for each patient that is required to address the clinical question.
- 4) The clinical question of interest in respect of **other intercurrent events** not covered through the precise specifications of treatment, population and variable.
- 5) A **population-level summary** for the variable providing a basis for comparison between treatment conditions.

#### 4.1.1. Treatment Condition of Interest

The primary treatment condition of interest is abelacimab administered s.c. once monthly and is compared against the alternative treatment condition of rivaroxaban p.o. administered once per day.

#### 4.1.2. Population of Patients Targeted by the Clinical Question

The population targeted by the clinical question is defined through the inclusion and exclusion criteria as part of the clinical trial protocol version 5.1.

#### 4.1.3. Variable Obtained from Each Patient Required to Address the Clinical Question

For each patient in the study, the variable to address the clinical question is time from randomization to first event of composite of ISTH-defined major bleeding or CRNM bleeding events. Patients still alive and on study without an event will be censored at the EoT date. Patients lost to follow-up or who otherwise discontinued follow-up in the study prematurely without experiencing any event will be censored at the EoT date, as defined in Section 3.1. For patients who die without experiencing a primary event before death, the time to event will be censored on the date of death.

#### 4.1.4. Handling of Intercurrent Events to Reflect the Clinical Question of Interest

Intercurrent events will be handled through a treatment policy strategy.

The following intercurrent events are anticipated during the study:

- Death
- Treatment discontinuation
- Study discontinuation
- Concomitant anticoagulation therapy

**Table 1** describes how intercurrent events will be collected and handled within the analysis.

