### 3. Analysis Populations and Dates

#### 3.1. Analysis Dates

The analysis dates to be used are defined as:

- EoT date = Earliest of a) the last dose+60 days or b) the EoT visit or c) death date or d) withdraw consent date or e) EoS visit date
- EoS date = Earliest of a) EoS visit or b) death date or c) withdraw consent date or d) lost to follow-up date; if no EoS date available, then impute EoT visit date

In the event that there is an open-label extension period in which the patient enrolls, the following analysis dates to be used are defined as:

- EoT date = Earliest of a) the last dose+60 days or b) the EoT visit or c) death date
- EoS date = Earliest of a) the last dose+60 days or b) the EoT visit or c) death date
- EoE date = Earliest of a) the last dose+60 days or b) the EoE visit or c) death date
- EoS extension date = EoS visit; if no EOS visit date available, then impute EoE date

In accordance with ICH E3 and E9, the following analysis sets will be used for the analyses.

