**Table 1. Handling of Intercurrent Events for the Primary Estimand**

Intercurrent event	Data collection and analysis
Treatment discontinuation	Events occurring up until the EoT date will be included in the analysis. Patients without event will be censored at the EoT date.
Study discontinuation	Events occurring up until the EoT date will be included in the analysis. Patients without event will be censored at the EoT date.
Concomitant anticoagulation therapy	Patients who use concomitant anticoagulation and continue on study will be analyzed by the treatment policy strategy, i.e., no adjustment will be made. Patients who use concomitant anticoagulation without a primary event before the EoT date will be censored at the EoT date.
Death	Patients who experienced primary event before death will be included in the analysis. Patients who did not experience any bleeding event before death will be censored at the time of death reflecting a while alive strategy.

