## 6.6. Primary Analysis

### 6.6.1. Primary Analysis

The primary endpoint variable is defined as time to first event of composite of ISTH-defined major bleeding or CRNM bleeding events occurring from randomization through EoT date. Patients alive and on-study without an event will be censored at the EoT date. Patients lost to follow-up or who otherwise discontinued study follow-up prematurely without experiencing any event will be censored at the EoT date, as defined in Section 3.1. Patients who did not experience any event before death will be censored at the earlier of the date of death and EoT date.

The primary analysis will compare each abelacimab regimen with rivaroxaban for the time from randomization to first occurrence of major or CRNM bleeding in the On-Treatment Analysis Set. For each treatment regimen, the event rates at 6-month intervals will be estimated with 95% confidence intervals (CIs). For each comparison, the time to first event will be tested using the stratified log-rank test and the treatment effect estimated using the Cox proportional hazards model including treatment and the following two stratification factors as covariates:

- Planned use of concomitant antiplatelet medication use (e.g. aspirin and/or P2Y12 inhibitor) for the duration of the trial
- CrCl (Cockcroft-Gault)  $\leq 50$  ml/min

The hazard ratios with 95% CIs and two-sided p-values will be reported for both doses of abelacimab vs. rivaroxaban. A significance level of  $\alpha=0.05$ , without adjustment for multiplicative testing, will be used.

An inverted Kaplan-Meier plot will be drawn and estimates of the event rate at 6-month intervals will be presented.

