### 2.1. Change in the EoT date and EoS date in the randomized phase of the study for patients enrolled in the extension in section 3.1 of the SAP

The analysis dates to be used are defined as:

- EoT date = Earliest of a) the last dose+60 days or b) the EoT visit **-1 day** or c) death date or d) withdraw consent date or e) EoS visit date
- EoS date = Earliest of a) EoS visit or b) death date or c) withdraw consent date or d) lost to follow-up date; if no EoS date available, then impute EoT visit date **-1 day**

**As per the protocol version 5.0, EoT visit and Extension Day 1 will occur on same day.** In the event that there is an open-label extension period in which the patient enrolls, the following analysis dates to be used are defined as:

- EoT date = **Earlier of a) the last dose+60 days or b) the EoT visit -1 day**
- EoS date = **the EoT visit -1 day**
- EoE date = Earliest of a) the last dose+60 days or b) the EoE visit or c) death date
- EoS extension date = EoS visit; if no EOS visit date available, then impute EoE date

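### SAP 4.1.4 labels the primary estimand treatment policy, but after permanent discontinuation the analysis is while on treatment with a tail of at most 60 days; the ITT end date for these patients also needs stating.

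*SAP*

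**What the plan says.** **Label.** SAP 4.1.4 lists death, treatment discontinuation, study discontinuation and concomitant anticoagulation, and says of them all: "Intercurrent events will be handled through a treatment policy strategy".

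**Handling.** The Table 1 rows for treatment and study discontinuation read: "Events occurring up until the EoT date will be included in the analysis. Patients without event will be censored at the EoT date". SAP 3.1 sets the cut-off: "EoT date = Earliest of a) the last dose+60 days or b) the EoT visit or c) death date or d) withdraw consent date", with the EoS visit as a fifth limb. Addendum 2.1 moves the EoT visit limb back one day and keeps the 60-day cap and the remaining limbs: "or c) death date or d) withdraw consent date or e) EoS visit date". SAP 3.3 uses the same date for the primary analysis set: "Patients will be considered to be on-treatment through the EoT date as outlined in Section 3.1".

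**Death.** SAP 4.1.3 says: "For patients who die without experiencing a primary event before death, the time to event will be censored on the date of death". Table 1 agrees: "Patients who did not experience any bleeding event before death will be censored at the time of death reflecting a while alive strategy". SAP 6.6.1 says: "Patients who did not experience any event before death will be censored at the earlier of the date of death and EoT date".

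**ITT window.** SAP 6.6.2 runs the ITT sensitivity analysis to the EoS date, which SAP 3.1 and Addendum 2.1 define as the earliest of an EoS visit, death, consent withdrawal and loss to follow-up. Protocol 6.6 gives permanent stoppers an EoS visit about 30 days after the permanent study drug discontinuation (PSDD) visit. Telephone contacts for endpoints then continue about every 12 weeks until the randomized period ends.

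**The concern.** A treatment-policy estimand counts bleeding whether or not the patient stays on drug. The primary analysis stops counting soon after permanent discontinuation. Someone who relies on the estimand section would therefore take the hazard ratio to answer a broader question than it does. SAP 4.2 defines the secondary estimands in the same way as the primary, so the label carries over to them.

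The ITT end date matters because ITT is the only listed sensitivity analysis of the primary endpoint that runs past the EoT date. If it ends at the early EoS visit, endpoint data already collected from stoppers are left out, and ITT adds little or nothing for the patients in whom the two strategies differ.

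**Working it through.** **1. Label against handling, event by event**

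| Intercurrent event | SAP 4.1.4 | What Table 1, 3.1 and 6.6.1 do |
|---|---|---|
| Permanent treatment discontinuation | Treatment policy | While on treatment, to the EoT date (last dose + 60 days at the latest) |
| Study discontinuation | Treatment policy | Censoring at the EoT date; follow-up has ended, so this is missing data, not a strategy |
| Concomitant anticoagulation | Treatment policy | Treatment policy, to the EoT date |
| Death | Treatment policy | Named while alive |

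Only the anticoagulation row matches the general sentence. Temporary interruptions (Protocol 6.5, no limit on number or length) stay in the risk set once dosing resumes, because the EoT date is counted from the last dose. The mismatch is therefore confined to permanent stopping.

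**2. Death rule**

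Take an event-free patient with last dose on day 100, EoT date day 160 and death on day 300. SAP 6.6.1 censors at day 160; 4.1.3 and Table 1 censor at day 300. Since 6.6.1 counts events only to the EoT date, the second rule adds 140 days of risk time in which no event can count. SAP 6.6.3 applies the 6.6.1 procedures to the secondary endpoints, while 4.2 points them to the Section 4.1 wording.

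Size, by simulation: stopping at 5-20% per year, death at 2-5% per year (both assumed), EoT date 30 or 60 days after stopping, and the follow-up in step 4. About 1-17 of 1,287 patients are affected, with 0.02-0.56% of on-treatment person-time.

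**3. Which EoS visit ends ITT?**

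- *Early reading.* The only EoS visit that Protocol 6.6 schedules for permanent stoppers is about 30 days after PSDD, and the SAP takes the earliest date. If PSDD is p days after the last dose, the EoS visit is at p + 30 and the EoT date at min(60, p + 30). ITT then adds max(0, p − 30) days: none at p = 20, 15 days at p = 45. The documents do not give p.
- *End-of-trial reading.* Protocol 10.1 runs ITT through the EoS of the randomized period. Protocol 5 follows all randomized patients to the EoS visit even if they stopped drug. Protocol 7.4 delays loss-to-follow-up status until the scheduled end-of-study visit would have occurred. Protocol 6.6 holds back completion status until the study is declared complete, and SAP 6.2 reads completion from that status.

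Addendum 2.1 fixes the EoS date only for extension enrollees (EoT visit − 1 day).

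**4. Illustrative size**

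Inputs from the documents: 1,287 randomized, enrolment complete December 2021, longest follow-up 1.5 years at September 2022 (Protocol 1.2.2); hazard ratio 0.60, 15% per year on rivaroxaban, 10% annual dropout, 27 months (SAP 2.3). Assumed: stopping rate r of 5, 10 or 20% per year, and bleeding at the rivaroxaban rate in all arms from 60 days after stopping.

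The plan's 166 events are not in dispute and reproduce. The pairwise share is 166 × 1.60/2.20 = 120.7. Then √(120.7/4) × |ln 0.60| − 1.96 = 0.85, a power of 80.1%.

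Follow-up is taken as uniform: 0.75-1.5 years at September 2022 (mean 13.5 months, consistent with the stated mean above 12 months) and 1.5-2.25 years at month 27.

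- Share stopped, for follow-up uniform on (a, b): 1 − [exp(−ra) − exp(−rb)] / [r(b − a)]. For r = 0.05 on (0.75, 1.5): 1 − (0.96319 − 0.92774)/0.0375 = 5.5%, or 70 patients.
- Person-time later than 30 days after stopping (PSDD on the day of stopping): mean of ∫ from 30 days to T of [1 − exp(−r(t − 30 days))] dt, divided by mean T.
- Treatment-policy hazard ratio: the limiting Cox estimate, solving ∫[e_A − (e_A + e_R) n_A θ/(n_A θ + n_R)] dt = 0 for θ, where n is the expected number at risk and e the expected event rate. The hazard is 0.15 on rivaroxaban; on abelacimab it is 0.09, rising to 0.15 from 60 days after stopping.

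| Cut | r per year | Stopped | Person-time outside ITT, early reading | Treatment-policy HR |
|---|---|---|---|---|
| Sept 2022 | 5% | 5.5% (70) | 2.5% | 0.608 |
| Sept 2022 | 10% | 10.6% (137) | 4.9% | 0.615 |
| Sept 2022 | 20% | 20.1% (258) | 9.4% | 0.630 |
| Month 27 | 5% | 8.9% (115) | 4.2% | 0.614 |
| Month 27 | 10% | 17.1% (220) | 8.2% | 0.627 |
| Month 27 | 20% | 31.2% (402) | 15.4% | 0.651 |

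Counting only time at risk for a first event, after dropout, the person-time range becomes 2.3-14.0%.

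**The case against.** The sponsor can say that 4.1.4 sends the reader straight to Table 1, which states the EoT cut-off, and that the protocol synopsis, Protocol 10.4, SAP 3.3 and SAP 6.6.1 all name the On-Treatment set. No analyst would compute a different hazard ratio, and the death mismatch is close to editorial. This stands as far as the computation goes. It does not rescue the label: 4.1.4 makes a statement about the estimand that Table 1 contradicts, and the discontinuation row of Table 1 names no strategy that would correct it.

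Three stronger readings are tempting, and the documents do not support them.

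- *That the primary analysis is inconsistent or the hazard ratio needs recomputing.* The operative text is consistent; only its description is wrong.
- *That ITT was cut at the early visit.* Several protocol provisions favour an end-of-trial date, so this is an ambiguity and not a proven error. Even on the early reading, the claim that ITT adds no follow-up needs PSDD within 30 days of the last dose. With monthly injections, and an interruption form required only beyond 45 days from the previous dose, PSDD may come later.
- *That the plan contains no treatment-policy estimate.* The exploratory analyses are redacted, so this cannot be asserted.

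**Conclusion.** The point holds and should be corrected. For permanent discontinuation the treatment-policy label is wrong for the primary estimand and, through SAP 4.2, for the secondary ones. The primary hazard ratio is unaffected, but what it may be said to estimate narrows to an on-treatment effect. The death wording is a minor inconsistency with negligible numerical effect. The ITT end date for permanent stoppers is unresolved and should be settled in writing.

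The gap between the two strategies, 0.60 against about 0.61-0.65, is an illustration. It depends on assumed stopping rates, post-stop bleeding at the rivaroxaban rate and uniform follow-up. On an end-of-trial EoS date, ITT would show that gap; on the early date, ITT would stay near 0.60. Confidence is high for the label and death wording and moderate for the EoS date.

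**What to change.** 1. In SAP 4.1.4 and Table 1, name the strategy per event. Permanent treatment discontinuation: while on treatment to the EoT date as amended, with temporary interruptions kept in the risk set. Concomitant anticoagulation: treatment policy to the EoT date. Death: while alive to the EoT date. Describe withdrawal and loss to follow-up as censoring. Describe the primary and secondary hazard ratios as on-treatment effects.
2. Put the 6.6.1 death rule into 4.1.3 and the Table 1 death row.
3. In SAP 3.1, state that for permanent stoppers ITT follow-up runs to the last endpoint contact up to the end of the randomized period, or to death or consent withdrawal if earlier. Keep the EoT visit − 1 day rule for extension enrollees. If the early EoS visit was used, rerun ITT on the data already collected.

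**Cost.** A few sentences, documented as a post-lock change (database lock 08Mar2024). No new data are needed, and there is no rerun unless the early visit was used. Any rerun ITT estimate would be defined after lock and must be labelled so.
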